7.0 TRIAL PROCEDURES

7.1 TRIAL PROCEDURES

The Trial Flow Chart - Section 6.0 summarizes the trial procedures to be performed at each visit. Individual trial procedures are described in detail below. It may be necessary to perform these procedures at unscheduled time points if deemed clinically necessary by the investigator.

7.2 MEDICAL HISTORY

A medical history will be obtained by the investigator or qualified designee. Medical history will include all active conditions, and any condition diagnosed within the prior 10 years that are considered to be clinically significant by the Investigator. Details regarding the disease for which the subject has enrolled in this study will be recorded separately and not listed as medical history.

7.3 PRIOR AND CONCOMITANT MEDICATIONS REVIEW

7.3.1 PRIOR MEDICATIONS

The investigator or qualified designee will review prior medication use, including any protocol-specified washout requirement, and record prior medication taken by the subject within 28 days before starting the trial. Treatment for the disease for which the subject has enrolled in this study will be recorded separately and not listed as a prior medication.

7.3.2 CONCOMITANT MEDICATIONS

The investigator or qualified designee will record medication, if any, taken by the subject during the trial. All medications related to reportable SAEs should be recorded as defined in Section 8.

7.4 DISEASE DETAILS AND TREATMENTS

7.4.1 DISEASE DETAILS

The investigator or qualified designee will obtain prior and current details regarding disease status.

7.4.2 PRIOR TREATMENT DETAILS

The investigator or qualified designee will review all prior cancer treatments including systemic treatments, radiation and surgeries.

7.4.3 SUBSEQUENT ANTI-CANCER THERAPY STATUS

The investigator or qualified designee will review all new anti-neoplastic therapy initiated after the last dose of trial treatment. If a subject initiates a new anti-cancer therapy within 30 days after the last dose of trial treatment, the 30-day Follow-up visit must occur before the first dose of the new therapy. Once new anti-cancer therapy has been initiated the subject will move into survival follow-up.

7.4.4 ASSIGNMENT OF SCREENING/STUDY NUMBER

All consented subjects will be given a unique screening number that will be used to identify the subject for all procedures that occur prior to eligibility being confirmed. Protocol treatment must begin only after eligibility criteria are confirmed by the UC PI. Sites must provide notification of consent and evidence of eligibility to the UC PI. Each subject will be assigned only one screening

number. Screening numbers must not be re-used for different subjects. The University of Cincinnati will provide any sub-sites with instructions for the methods to be used in assigning screening information to potential subjects.

Any subject who is screened multiple times will retain the original screening number assigned at the initial screening visit. The screening number will be their study number as well once they are allocated to treatment.

7.4.5 TRIAL COMPLIANCE

Interruptions from the protocol specified treatment plan for greater than 8 weeks' delay of Nivolumab doses require consultation between the investigator and the University of Cincinnati PI (if not the same) and written documentation of the collaborative decision on subject management.

The total volume of Nivolumab infused will be compared to the total volume prepared to determine compliance with each dose of Nivolumab administered. The preparing and administering Nivolumab should be completed per the latest IB. Treatment with standard therapies will be prepared and administered as per the approved product label.

7.5 CLINICAL PROCEDURES/ASSESSMENTS

7.5.1 ADVERSE EVENT (AE) MONITORING

The investigator or qualified designee will assess each subject to evaluate for potential new or worsening AEs as specified in the Trial Flow Chart and more frequently if clinically indicated. Adverse events will be graded and recorded throughout the study and during the follow-up period according to NCI CTCAE Version 5.0. Toxicities will be characterized in terms regarding seriousness, causality, toxicity grading, and action taken with regard to trial treatment.

Please refer to section 8 for detailed information regarding the assessment and recording of AEs.

7.5.2 FULL PHYSICAL EXAM

The investigator or qualified designee will perform a full physical exam during the screening period. Clinically significant abnormal findings should be recorded as medical history. Full physical exam requires assessment of major organ sites (Constitutional, Head and Neck, Cardiovascular, Pulmonary, Abdominal, Musculoskeletal, Lymph, Neurological, and Skin).

7.5.3 DIRECTED PHYSICAL EXAM

For cycles that do not require a full physical exam per the Trial Flow Chart, the investigator or qualified designee will perform a directed physical exam as clinically indicated prior to trial treatment administration.

7.5.4 VITAL SIGNS

The investigator or qualified designee will take vital signs at screening, prior to the administration of each dose of trial treatment and at treatment discontinuation as specified in the Trial Flow Chart. Vital signs should include temperature, pulse, respiratory rate, weight and blood pressure. Height will be measured at screening only.

7.5.5 EASTERN COOPERATIVE ONCOLOGY GROUP (ECOG) PERFORMANCE SCALE

The investigator or qualified designee will assess ECOG status (see Section 11 Appendix 1) at screening, prior to the administration of each dose of trial treatment and discontinuation of trial treatment as specified in the Trial Flow Chart.

7.5.6 TUMOR IMAGING AND ASSESSMENT OF DISEASE

Pre-operative imaging will be performed at each institution and only site investigators (PI or Sub-PIs) may determine the assessment of disease recurrence.

7.5.7 POST-TREATMENT ASSESSMENT IMAGING

Patients will be followed clinically for recurrence every three months. Imaging is not required unless there is suspicion of relapsed disease and is needed for assessment.

7.5.8 ASSESSMENT OF DISEASE

Patients will be assessed for recurrence every 3 months after completion of treatment as above. For patients felt to have a relapse at any time, a thorough ENT exam as well as a repeat biopsy is recommended to confirm relapsed disease. Follow-up imaging in 4-8 weeks is also acceptable if biopsy is not yet felt to be necessary or is non-diagnostic. Patients will be followed clinically every three months and any concern for relapsed disease or progression should trigger either imaging or biopsy for confirmation. Patients will be followed for relapse for a total of 2 years.

7.6 TUMOR TISSUE COLLECTION AND CORRELATIVE STUDIES BLOOD SAMPLING

Any subjects with oropharyngeal cancers must have documented HPV status (either by p16 or in situ hybridization).

Resected tissue, preferably a tissue block (at least 20, but prefer 30, FFPE slides and a tissue scroll if block not feasible) must be submitted and delivered to UCCI for analyses. If patient develops recurrence and undergoes standard of care biopsy or resection, the tissue will also be collected for analysis similar to above. Please see laboratory procedures manual for full details.

Blood samples will be collected at screening after resection and after first adjuvant dose of Nivolumab at week 5. A third collection will be collected at the 30 day post-discontinuation visit.

Detailed processing, shipping and handling will be provided in the laboratory procedures manual.

7.6.1 LABORATORY PROCEDURES/ASSESSMENTS

Details regarding specific laboratory procedures/assessments to be performed in this trial are provided below.

7.6.2 LABORATORY SAFETY EVALUATIONS (HEMATOLOGY, CHEMISTRY AND URINALYSIS)

Laboratory tests for hematology, chemistry, urinalysis, and others are specified in Table 3.

Table 3. Laboratory Test

7.6.3 PHARMACODYNAMIC EVALUATIONS

Please refer to the Laboratory Manual for PBMC Procedures.

Hematology	Chemistry	Urinalysis	Other
Hematocrit	Albumin	Blood	Serum β -human chorionic gonadotropin†
Hemoglobin	Alkaline phosphatase	Glucose	(β -hCG)†
Platelet count	Alanine aminotransferase (ALT)	Protein	Total triiodothyronine (T3)
WBC (total and differential)	Aspartate aminotransferase (AST)	Specific gravity	Free tyroxine (T4)
Red Blood Cell Count	Lactate dehydrogenase (LDH)	Microscopic exam (If abnormal)	Thyroid stimulating hormone (TSH)
Absolute Neutrophil Count	(CO_2 or biocarbonate)	Urine pregnancy test †	Prothrombin time PT/INR
Absolute Lymphocyte Count	Uric Acid		Partial Thromboplastin Time (PTT)
	Calcium		
	Chloride		Blood for correlative studies
	Glucose		
	Phosphorus		
	Potassium		
	Sodium		
	Creatinine		
	Magnesium		
	Total Bilirubin		
	Direct Bilirubin (If total bilirubin is elevated above the upper limit of normal)		
	Total protein		
	Blood Urea Nitrogen		
	Blood Urea Nitrogen		
† Done on all women of child-bearing potential			

Immunohistochemistry/Immunofluorescence

Archived resected tissue and if available recurrent biopsy or surgical tissue will be sent to the University of Cincinnati pathology department for processing. FFPE sections will be used to analyze the immune cell phenotype (markers include CD4, CD8, T reg, PD-1, PD-L1, granzyme expression and KI-67).

RNA Sequencing for Inflammatory Gene Signature

FFPE tissue will also undergo RNA and/or whole exome sequencing to identify an inflammatory gene signature and possible genetic alterations in responders versus non-responders.

7.6.4 WITHDRAWAL/DISCONTINUATION

When a subject discontinues/withdraws prior to trial completion, all applicable activities scheduled for the final trial visit should be performed at the time of discontinuation. Any adverse events, which are present at the time of discontinuation/withdrawal, should be followed in accordance with the safety requirements outlined in Section 8.

7.7 VISIT REQUIREMENTS

Visit requirements are outlined in Section 6.0 - Trial Flow Chart.

7.7.1 SCREENING

Potential subjects will be evaluated to determine that they fulfill the entry requirements as set forth in eligibility requirements. Visit requirements are outlined in Section 6.0 – Trial Flow Chart.

Results of a test performed prior to the subject signing consent as part of routine clinical management are acceptable in lieu of a screening test if performed within the specified time frame. Screening procedures are to be completed within 28 days prior to the first dose trial treatment except for the following:

- Laboratory tests and ECOG PS are to be performed within 10 days prior to the first dose of trial treatment.
- For women of reproductive potential, a serum pregnancy test will be performed within 72 hours prior to the first dose of trial treatment. A urine test may be considered if serum test is not appropriate.
- Any tumor imaging done pre-operatively, does not need to meet the 28 day pre-dose requirement for screening procedures

Subjects may be rescreened after initially failing to meet the inclusion/exclusion criteria and they have not yet started treatment, however, re-screening tests will not be covered by study. Results from assessments performed during the initial screening period are acceptable in lieu of a repeat screening test if performed within the specified time frame and the inclusion/exclusion criteria is met. Protocol treatment must begin only after eligibility criteria are confirmed by the UC PI.

7.7.2 TREATMENT PERIOD

Visit requirements are outlined in Section 6.0 – Trial Flow Chart.

7.7.3 POST-TREATMENT VISITS/SAFETY FOLLOW-UP VISIT

The mandatory 30 day Safety Follow-Up Visit should be conducted based on one of the following time points. The time point which occurs first must be used to determine the safety follow-up visit timing.

- Approximately 30 days after the last dose of trial treatment or
- Approximately 30 days post-discontinuation if this occurs prior to the planned end of treatment or
- Before the initiation of a new anti-cancer treatment.

All AEs that occur prior to the Safety Follow-Up Visit should be recorded. Subjects with an AE of Grade > 1 will be followed until the resolution of the AE to Grade 0-1 or until the beginning of a new anti-neoplastic therapy, whichever occurs first. SAEs that occur within 100 days of the end of treatment or before initiation of a new anti-cancer treatment should also be followed and recorded.

7.7.4 FOLLOW-UP VISITS

Patients will move into follow-up after completion of last dose of Nivolumab. They will continue follow-up every 12 weeks +/- 4 weeks either by a doctor visit or by phone (if being seen by outside oncologist) for up to 2 years to monitor for relapse, or until time of withdrawal of consent, or death, whichever comes first. If patients develop a relapse, they will be followed for survival. Every effort should be made to confirm relapse if suspected.

7.7.5 SURVIVAL FOLLOW-UP

Once a subject experiences confirmed disease relapse/progression or starts a new anti-cancer therapy, the subject moves into the survival follow-up phase and should be contacted by telephone or seen in clinic every 12 weeks +/- 4 weeks to assess for survival status until death, withdrawal of consent, or at the end of the study, whichever occurs first.

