All patients who received ≥ 1 dose of Nivolumab will be assessed for efficacy and the primary and secondary endpoints for efficacy will be disease-free survival (DFS) at 2- and 1-year, respectively. DFS is defined as the duration from the time of treatment allocation to the time of discovery of the first evidence after initiation of investigational treatment of any tumor (local, regional, metastatic, or second primary) or death from any cause. The distribution of DFS will be summarized by Kaplan-Meier curve, and the median DFS and its associated 95% confidence interval (CI) will be calculated. The DFS at 1- and 2-years will also be summarized with its associated 95% CIs. In addition, patients will be censored at the end of the study (end of two years of follow-up of last patient enrolled), and both disease free survival (or DFS defined as no recurrence by the time of censoring) and overall survival (OS, defined as being alive by the time of censoring) will be assessed using Kaplan-Meier curves.

Safety Analyses:

The All-Patients-as-Treated (APaT) population will be employed for safety analyses. The secondary safety endpoints are the Grade 3 and 4 adverse events and the all adverse event graded from 1 to 5. Both safety secondary endpoints are dichotomous and will be summarized using frequency (in %). In addition, the 95% CI's will be calculated using the exact method, i.e. the binomial distribution method. We expect to reach 13% of Grade 3 and 4 adverse events and 58.9% of all Graded Adverse events, similar to those reported in the Checkmate 141 study.

Biomarker Assessments:

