4.5 SUBJECT WITHDRAWAL/DISCONTINUATION CRITERIA

Subjects may withdraw consent at any time for any reason or be dropped from the trial at the discretion of the investigator. In addition, a subject may be withdrawn by the investigator if enrollment into the trial is inappropriate, the trial plan is violated, or for administrative and/or other safety reasons.

The End of Treatment and Follow-up visit procedures are listed in Section 6 (Protocol Flow Chart) and Section 7.9 (Visit Requirements). After the end of treatment, each subject will be followed for 30 days for adverse event monitoring (serious adverse events will be collected for 100 days after the end of treatment). Subjects who discontinue for reasons other than progressive disease will have post-treatment follow-up for disease status until disease progression, initiating a non-study cancer treatment, withdrawing consent or becoming lost to follow-up or the end of the study whichever occurs first. After documented disease progression each subject will be followed by telephone for overall survival until death, withdrawal of consent, or the end of the study, whichever occurs first.

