9.6 STATISTICAL METHODS

9.6.1 DISEASE FREE SURVIVAL

The distributions of DFS will be summarized using the Kaplan-Meier (KM) curves and the median DFS and its associated 95% CIs will be estimated. The DFSs at 1- and 2-year will be also summarized with its associated 95% CIs. In addition, KM curves will be used to assess DFS and OS of the patients. Median survival time and its associated 95% CI will be estimated from the KM curves.

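### The follow-up sections disagree on how long relapse-free patients are followed, which leaves the Kaplan–Meier OS curve open to bias beyond about 2 years

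*Combined protocol and SAP*

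**What the plan says.** Relapse-free patients:

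- Section 7.5.8: "Patients will be followed for relapse for a total of 2 years".
- Section 7.7.4 starts the follow-up period after the last nivolumab dose and continues contacts "for up to 2 years to monitor for relapse, or until time of withdrawal of consent, or death, whichever comes first".
- Section 4.5 has no 2-year limit: "Subjects who discontinue for reasons other than progressive disease will have post-treatment follow-up for disease status until disease progression", with the other stopping points being a non-study cancer treatment, "withdrawing consent or becoming lost to follow-up or the end of the study whichever occurs first". Note q to the flow chart (section 6.0) repeats this.
- The Synopsis (Study Design) has 3-monthly follow-up for disease and survival status with no stated end. The flow chart has a 12-weekly row for survival and disease status, by phone or clinic, that is not restricted to relapsed patients.

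Relapsed or new-therapy patients:

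- Section 7.7.5: "Once a subject experiences confirmed disease relapse/progression or starts a new anti-cancer therapy, the subject moves into the survival follow-up phase", with contact every 12 weeks "to assess for survival status until death, withdrawal of consent, or at the end of the study, whichever occurs first".

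Analysis:

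- The Synopsis (Efficacy Analyses) says "patients will be censored at the end of the study (end of two years of follow-up of last patient enrolled", and plans Kaplan–Meier curves for DFS and OS in all patients with at least one dose. Section 9.1 agrees, without defining end of study.
- Section 9.6.1 adds: "Median survival time and its associated 95% CI will be estimated from the KM curves".
- No section gives the date at which OS is censored for a patient who is no longer contacted, and none limits the OS curve to a fixed time.

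**The concern.** Kaplan–Meier assumes that a patient's censoring time carries no information about risk of death. Under 7.5.8, 7.7.4 and 7.7.5 together, a patient who entered early and stays relapse-free leaves observation at the cap, while one who relapsed stays under observation to end of study. Relapse strongly predicts death, so beyond the cap OS censoring would depend on prognosis. If OS is censored at last contact, the curve then falls at roughly the death rate of relapsed patients, and a median lying beyond the cap is estimated too early or reported as reached when it has not been. The more patients stay relapse-free, the more low-risk patients leave at the cap, so the distortion grows if the drug works. The trial has two institutions, and one could follow 7.7.4 while the other follows 4.5.

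**Working it through.** **1. Time window.** Accrual at 3–4 patients per month: 39/4 = 9.75 and 39/3 = 13 months, which reproduces the plan's 10–13 months. End of study is 24 months after the last entry, so the first patient is observable for 33.75–37 months. The plan states no OS figure to reproduce.

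**2. Where the cap falls.** Section 7.5.8 gives 2 years in total, taken here as month 24 from first dose. Section 7.7.4 counts from the last dose. The sixth dose is at week 21, 20 weeks after the first: 20 × 7/30.44 = 4.6 months, so the cap is about month 28.6.

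**3. Model.** Constant rates per month: λ for any DFS event, r for relapse, μ for death after relapse. Then

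OS(t) = e^(−λt) + [r/(μ−λ)]·[e^(−λt) − e^(−μt)].

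If relapse-free patients are censored at cap c and relapsed patients are not, the Kaplan–Meier curve for t > c tends to OS(c)·e^(−μ(t−c)). Up to c it equals OS(t).

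**4. Scenarios.** The 2-year DFS values are the plan's (33% null, 53% alternative). The other inputs are assumptions, except where noted.

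- A: DFS 53%, λ = −ln(0.53)/24 = 0.02645; relapse-free death 0.003, so r = 0.02345; median survival after relapse 12 months, μ = ln2/12 = 0.05776. OS(24) = 0.740, OS(28.6) = 0.677, OS(30) = 0.659. With the 24-month cap: 0.740 × e^(−0.05776×6) = 0.740 × 0.707 = 0.523. With the 28.6-month cap: 0.677 × e^(−0.05776×1.4) = 0.677 × 0.922 = 0.62.
- B: DFS 53%, 10% of DFS events are deaths without relapse, r = 0.9λ = 0.02381; 2-year OS 70%, which gives μ = 0.0803.
- C: DFS 33%, λ = 0.04619, r = 0.9λ = 0.04157; 2-year OS 57%, from the 12 deaths among 28 historical patients in section 2.1 (16/28), which gives μ = 0.0735.

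| Scenario | 30-month OS: true | 24-month cap | 28.6-month cap | Median OS: true | 24-month cap | 28.6-month cap |
|---|---|---|---|---|---|---|
| A | 0.66 | 0.52 | 0.62 | 42.8 | 30.8 | 33.9 |
| B | 0.61 | 0.43 | 0.56–0.57 | 38.6 | 28.2 | 31.5 |
| C | 0.46 | 0.37 | 0.44 | 27.9 | 25.8 | 27.9 |

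Medians (months) under a cap are c + ln(OS(c)/0.5)/μ when OS(c) > 0.5; in B, 24 + ln(0.700/0.5)/0.0803 = 28.2. The true medians in A and B lie beyond the longest possible follow-up of 37 months, so with complete follow-up they would usually not be reached.

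**5. Sensitivity.** In A with the 24-month cap, a post-relapse median of 9 months gives 0.703 × 0.630 = 0.44 against 0.62, and 18 months gives 0.789 × 0.794 = 0.63 against 0.72. If 2-year OS were 42%, the median (20.1 months) would precede either cap and be unaffected.

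**6. Trials of 39 patients.** Simulating A over the stated accrual range, the median is reported as reached in 56–68% of trials with the 24-month cap and 33–52% with the 28.6-month cap, against 13–25% when everyone is followed to end of study. Across the scenarios examined, the number at risk one month after a 24-month cap drops from about 14–25 to about 3–8 of 39.

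**7. The other censoring rule.** If relapse-free patients are no longer contacted but are counted alive to end of study, scenario A at 30 months gives 0.530 + (0.740 − 0.530) × 0.707 = 0.678 against 0.659. The error is then upward, here by about 0.02.

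**The case against.** A reader might infer that survival contact after 2 years definitely continues only for relapsed patients, and that the OS curve and its median therefore rest on relapsed patients and are biased downward. The documents do not support that.

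- The 2-year limits in 7.5.8 and 7.7.4 are worded as limits on relapse monitoring. Section 4.5, note q, the Synopsis and the flow-chart row can all be read as following relapse-free patients to end of study, and on that reading there is no bias.
- Every treated patient is in the efficacy set and at risk up to the cap, so the curve to 24 months, including 1- and 2-year OS, is not affected.
- Section 7.7.5 also keeps patients who start new therapy, so even the tail is not relapsed patients alone.
- Section 7.7.4's own cap is about month 28.6, where the distortion at 30 months is much smaller and the median in the historical scenario does not move.
- A downward direction assumes censoring at last contact. The Synopsis can be read as censoring at end of study, which reverses it.
- OS is not listed as a primary, secondary or exploratory endpoint, and has no hypothesis or decision rule.

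All of this stands, and it limits the point. It does not remove it. Section 4.5 and note q are worded for patients who discontinue, so whether they cover those who complete six doses is unclear. They also tie telephone follow-up for OS to documented progression. The stated rules still conflict, and the OS censoring date is undefined.

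**Conclusion.** The concern holds in limited form. The sections on follow-up of relapse-free patients contradict each other. If sites apply 7.5.8 or 7.7.4 and OS is censored at last contact, the OS tail beyond the cap is biased downward, as is the median if it falls there. At 2-year DFS of 53% with a 12-month post-relapse median, 30-month OS is about 0.52 against 0.66 with a 24-month cap, and 0.62–0.63 against 0.66 with a 28.6-month cap. The median is reported as reached too often under both caps.

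Whether the median is exposed is uncertain. The historical 12/28 deaths imply an exponential median near 24 × ln(0.5)/ln(16/28) = 29.7 months, which is after either cap, whereas scenario C puts it at 27.9, between the two.

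The sizes rest on constant hazards, assumed mortality before and after relapse, and accrual as planned. The need to reconcile the text does not. The primary DFS test is untouched by this point and OS is descriptive, so this is a minor point.

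**What to change.** 1. Reconcile 4.5, flow-chart note q, 7.5.8, 7.7.4 and 7.7.5, with the Synopsis and the flow-chart row, on how long relapse-free patients are followed. State whether the 2 years run from first or last dose, and whether patients who complete treatment are covered.
2. Require vital status for every treated patient, relapsed or not, at a common end-of-study cut-off.
3. State in 9.1 and 9.6.1 that OS is censored at the last date known alive.
4. If vital status will not be collected on everyone, truncate the OS curve and all OS summaries at the follow-up cap.

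Items 1, 3 and 4 need wording only. Item 2 costs a few telephone calls per relapse-free patient, 12-weekly for at most about a year after the cap.
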